5.3.5.8 Preexisting Medical Conditions

A pre-existing medical condition is one that is present at the screening visit for this study. Such conditions should be recorded on the General Medical History and Baseline Conditions eCRF.

A pre-existing medical condition should be recorded as an adverse event only if the frequency, severity, or character of the condition worsens during the study. When recording such events on the Adverse Event eCRF, it is important to convey the concept that the pre-existing condition has changed by including applicable descriptors (e.g., "more frequent headaches").

5.3.5.9 Lack of Efficacy or Worsening of Influenza A Infection

Medical occurrences or symptoms of deterioration that are anticipated as part of influenza A should only be recorded as an adverse event if judged by the investigator to have unexpectedly worsened in severity or frequency or changed in nature at any time during the study. When recording an unanticipated worsening of influenza A on the Adverse Event eCRF, it is important to convey the concept that the condition has changed by including applicable descriptors (e.g., "accelerated influenza A").

5.3.5.10 Hospitalization or Prolonged Hospitalization

Any adverse event that results in hospitalization following initial discharge (i.e., in-patient admission to a hospital) or prolonged hospitalization (after the current study hospitalization) should be documented and reported as a serious adverse event (per the definition of serious adverse event in [Section 5.2.2](#)), except as outlined below.

The following hospitalization scenarios are not considered to be adverse events:

- Hospitalization for respite care
- Hospitalization for a pre-existing condition, provided that all of the following criteria are met:
 - The hospitalization was planned prior to the study or was scheduled during the study when elective surgery became necessary because of the expected normal progression of the disease
 - The patient has not experienced an adverse event

The following hospitalization scenarios are not considered to be serious adverse events, but should be reported as adverse events instead:

- Hospitalization that was necessary because of patient requirement for outpatient care outside of normal outpatient clinic operating hours

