1.2.2.1 Phase 1 Entry-into-Human Study (GV28916)

In the Phase 1 entry-into-human (EIH) study (GV28916), 21 healthy volunteers were given single IV doses of placebo (n =5) or MHAA4549A (n =16) at 1.5, 5, 15, or 45 mg/kg and followed for 120 days.

A total of 23 treatment-emergent adverse events (TEAEs) were reported by 13 of the 21 subjects (61.9%) who received one dose of the study medication. Nineteen of these TEAEs were reported by 10 of the 16 subjects (62.5%) who had received MHAA4549A and four TEAEs were reported by 3 of the 5 subjects (60.0%) who received placebo. The total number of TEAEs reported was similar in all dosing cohorts (four TEAEs per cohort), with the exception of the 5-mg/kg cohort, where seven TEAEs were observed. Overall, no notable trends were observed among dose levels or between subjects who received MHAA4549A and those who received placebo.

The most commonly reported TEAEs in subjects receiving MHAA4549A were headache (4 subjects) and oropharyngeal pain (2 subjects). The severity of TEAEs was primarily mild, with only two moderate TEAEs. No serious adverse events or dose-limiting toxicities were reported. Two clinical laboratory values were considered TEAEs (an increase in ALT in 1 subject who received 5 mg/kg MHAA4549A and an increase in creatinine phosphokinase [CK] in 1 subject who received placebo). Both results returned to normal within 10 days.

No safety issues were observed with respect to vital signs results or ECG measurements. For all clinical laboratory results, no relevant differences in mean values or deviations from baseline over time were observed in subjects receiving MHAA4549A doses as compared to placebo. No drug-emergent anti-therapeutic antibodies (ATAs) were detected in this study.

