3. STUDY DESIGN

3.1 DESCRIPTION OF STUDY

3.1.1 Overview of Study Design

This is a Phase 2b (GV29216), randomized, double-blind, placebo-controlled study designed to assess the safety and clinical activity of a single IV dose of 3600 mg MHAA4549A or a single IV dose of 8400 mg MHAA4549A in hospitalized patients with severe influenza A in combination with oseltamivir versus a comparator arm of placebo with oseltamivir. *A Sponsor-approved influenza test that includes influenza antigen test or influenza polymerase chain reaction (PCR) test must be used to diagnose influenza A infection for study eligibility.* This study is planned to take place in approximately 170 study centers globally.

Initially, GV29216 targeted enrollment into two treatment groups: a single IV dose of 3600 mg of MHAA4549A with oseltamivir or a single IV dose of placebo with oseltamivir.

[figure not shown]
In this version of the protocol, patients will be randomized 1:1:1 into three treatment groups: a single IV dose of 3600 mg of MHAA4549A with oseltamivir, a single IV dose of 8400 mg of MHAA4549A with oseltamivir, or a single IV dose of placebo with oseltamivir. *Patients will be stratified by country, PPV versus supplemental O₂ at randomization, and suspected or confirmed bacterial pneumonia versus no bacterial*

pneumonia based on the status at randomization. All patients must begin study drug infusion within 48 hours of hospital admission. In addition, all patients will receive oseltamivir as standard therapy for a minimum of 5 days (10 doses) starting no later than 12 hours after completion of study drug administration. Oseltamivir treatment for longer than 5 days is permitted based on local investigator discretion.

Hospitalized patients with an O₂ or PPV requirement will be evaluated for influenza A infection. Enrollment in this study requires ongoing treatment within 24 hours of hospital admission with one of the following:

- any PPV or
- any supplemental O₂ to maintain oxygen saturation (SpO₂) > 92% ([Section 3.3.2](#))

Patients on PPV should not exceed *approximately* 45% of the total patients enrolled in the study.

[figure not shown]

Safety evaluations will also be provided by an IMC and SOC, as defined in the IMC and SOC agreement (see [Section 3.1.2](#)). If after review of available study data, the IMC and SOC conclude that there is a significant toxicity or worsening disease associated with MHAA4549A, they may recommend stopping further enrollment in the study.

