5.2.2 Serious Adverse Events (Immediately Reportable to the Sponsor)

A serious adverse event is any adverse event that meets any of the following criteria:

- Fatal (i.e., the adverse event actually causes or leads to death)
- Life threatening (i.e., the adverse event, in the view of the investigator, places the patient at immediate risk of death)

This does not include any adverse event that had it occurred in a more severe form or was allowed to continue might have caused death.

- Requires or prolongs inpatient hospitalization (see [Section 5.3.5.10](#))
- Results in persistent or significant disability/incapacity (i.e., the adverse event results in substantial disruption of the patient's ability to conduct normal life functions)
- Congenital anomaly/birth defect in a neonate/infant born to a mother exposed to study drug

- Significant medical event in the investigator's judgment (e.g., may jeopardize the patient or may require medical/surgical intervention to prevent one of the outcomes listed above)

The terms "severe" and "serious" are not synonymous. Severity refers to the intensity of an adverse event (e.g., rated as mild, moderate, or severe, or according to Division of AIDS Table for Grading the Severity of Adult and Pediatric Adverse Events [DAIDS]; see [Section 5.3.3](#), [Appendix 8](#), and [Appendix 9](#)); the event itself may be of relatively minor medical significance (such as severe headache without any further findings).

Severity and seriousness need to be independently assessed for each adverse event recorded on the eCRF.

Serious adverse events are required to be reported by the investigator to the Sponsor immediately (i.e., no more than 24 hours after learning of the event; see [Section 5.4.2](#) for reporting instructions).

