5.3.1 Adverse Event Reporting Period

Investigators will seek information on adverse events at each patient contact. All adverse events, whether reported by the patient or noted by study personnel, will be recorded in the patient's medical record and on the Adverse Event eCRF.

After informed consent has been obtained **but prior to initiation of study drug**, only serious adverse events caused by a protocol-mandated intervention (e.g., invasive procedures such as biopsies, discontinuation of medications) should be reported (see [Section 5.4.2](#) for instructions for reporting serious adverse events).

After initiation of study drug, all adverse events, regardless of relationship to study drug, will be reported until *study completion* at the Day 60 visit or *until an* Early Discontinuation visit. After this period, the investigator should report any serious adverse events that are believed to be related to prior study drug treatment (see [Section 5.6](#)).

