5.3.5.4 Abnormal Laboratory Values

Not every laboratory abnormality qualifies as an adverse event. A laboratory test result must be reported as an adverse event if it meets any of the following criteria:

- Accompanied by clinical symptoms
- Results in a change in study treatment (e.g., dosage modification, treatment interruption, or treatment discontinuation)
- Results in a medical intervention (e.g., potassium supplementation for hypokalemia) or a change in concomitant therapy
- Clinically significant in the investigator's judgment (laboratory abnormalities should be repeated at the first opportunity and only considered clinically significant if they persist on repeat assessment)

It is the investigator's responsibility to review all laboratory findings. Medical and scientific judgment should be exercised in deciding whether an isolated laboratory abnormality should be classified as an adverse event. Investigators should promptly repeat any abnormal assessment or clinically significant laboratory result. Only those findings that remain clinically significant upon a repeat assessment will be considered adverse events.

If a clinically significant laboratory abnormality is a sign of a disease or syndrome (e.g., alkaline phosphatase and bilirubin $5 \times$ upper limit of normal [ULN] associated with cholestasis), only the diagnosis (i.e., cholestasis) should be recorded on the Adverse Event eCRF.

If a clinically significant laboratory abnormality is not a sign of a disease or syndrome, the abnormality itself should be recorded on the Adverse Event eCRF, along with a descriptor indicating if the test result is above or below the normal range (e.g., "elevated potassium," as opposed to "abnormal potassium"). If the laboratory abnormality can be characterized by a precise clinical term per standard definitions, the clinical term should be recorded as the adverse event. For example, an elevated serum potassium level of 7.0 mEq/L should be recorded as "hyperkalemia."

Observations of the same clinically significant laboratory abnormality from visit to visit should not be repeatedly recorded on the Adverse Event eCRF, unless the etiology changes. The initial severity of the event should be recorded, and the severity or seriousness should be updated any time the event worsens.

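### Two adverse-event recording sentences conflict with the protocol's own definitions: prolongation of the index stay may lose SAE status, and treated laboratory abnormalities may not be recorded as AEs

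*Combined protocol and SAP*

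**What the plan says.** All references are to the Version 7 protocol.

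**Hospitalization.** Section 5.2.2 lists the criteria that make an adverse event serious, any one of which is enough. One is "Requires or prolongs inpatient hospitalization", with a pointer to Section 5.3.5.10. That section covers admissions after the first discharge and then adds that "prolonged hospitalization (after the current study hospitalization) should be documented and reported as a serious adverse event". It describes itself as applying "per the definition of serious adverse event in" Section 5.2.2.

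**Laboratory values.** Section 5.3.5.4 gives four criteria and makes reporting as an adverse event compulsory when any one is met. The third is "Results in a medical intervention (e.g., potassium supplementation for hypokalemia) or a change in concomitant therapy". The fourth is clinical significance in the investigator's judgment, and it alone carries a condition that the abnormality persist on repeat. The next paragraph ends: "Only those findings that remain clinically significant upon a repeat assessment will be considered adverse events". Section 5.2.1 separately counts as an adverse event any laboratory deterioration that comes with symptoms or changes study or concomitant treatment, and asks for no repeat test.

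**Setting.** Section 3.1.1 states: "All patients must begin study drug infusion within 48 hours of hospital admission". Section 5.3.1 requires that after study drug is started "all adverse events, regardless of relationship to study drug, will be reported until" the Day 60 visit or early discontinuation.

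**The concern.** Each pair of statements can give two answers for the same event.

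On hospitalization, every patient is already an inpatient when dosed. Until discharge, an adverse event can meet the hospitalization criterion only by lengthening the current stay. If the parenthesis in 5.3.5.10 removes that route, the criterion does nothing during the days right after dosing.

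On laboratory values, the section's own example is at risk. Hypokalemia given potassium meets a compulsory reporting criterion. If the potassium is normal on repeat because it was replaced, the later sentence says that it is not an adverse event.

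The safety objective in Section 2.1 concerns the nature, frequency and severity of serious and non-serious adverse events. Earlier exposure was in 84 dosed healthy volunteers (Section 1.2.2), so this trial is a main source of safety information in severely ill patients. Sites that resolve the conflicts differently would produce counts that are not comparable, and sites that follow the narrower sentences would produce lower ones. SAEs are also a named input to the IMC and SOC review of the safety cohort (Section 3.1.1).

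**Working it through.** No figure in the plan depends on this point, so nothing is recomputed. The check sets the current passages side by side.

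**Hospitalization: an illustrative case.** Suppose an adverse event on Day 3, such as renal impairment, adds four days to the index stay.

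- Section 5.2.2: serious, because it prolongs inpatient hospitalization. No exception is made for the index stay.
- Section 5.3.5.10, parenthesis read as referring to stays later than the current one: not serious on this criterion.
- Section 5.3.5.10, parenthesis read as a stay extended beyond its expected length: serious, in agreement with 5.2.2.
- Section 5.3.1: reportable as an adverse event under either reading.

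So the two readings differ on seriousness, not on whether the event is reported at all. Three things follow from serious status: reporting within 24 hours (Section 5.4), evaluation as an SAE for expedited reporting (Section 5.7), and inclusion in the separate SAE listing and summary (Section 6.5). All three are lost under the literal reading unless the event meets another criterion in 5.2.2, such as being life-threatening or medically significant in the investigator's judgment.

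**Laboratory values: an illustrative case.** Suppose a low potassium is treated and is normal on repeat.

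- Section 5.2.1: an adverse event, because concomitant treatment changed.
- Section 5.3.5.4, third criterion: must be reported.
- Section 5.3.5.4, closing sentence of the repeat-assessment paragraph, read without restriction: not an adverse event.

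An abnormality with symptoms that clears before the repeat test gives the same split, through the first criterion.

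Two comparisons within the protocol suggest that the closing sentence is broader than intended. The list of criteria attaches persistence to the fourth criterion only. The parallel rule for vital signs (Section 5.3.5.5) has the same intervention criterion and no repeat-test condition.

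**What is retained.** Under Section 6.5, out-of-range laboratory values are identified and selected laboratory data are summarized by arm, whether or not an adverse event was recorded. Section 5.3.5.6 has its own compulsory rule for combined liver abnormalities, with no repeat condition. The laboratory loss is therefore the adverse-event record, not the value.

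**The case against.** The strongest reply is that both passages can be read without conflict.

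Section 5.3.5.10 invokes the definition in 5.2.2 and claims no precedence over it. Neither of its two lists of exceptions mentions prolongation of the index stay. If the prolongation clause covered only later admissions, it would add little to the clause before it on hospitalization after discharge. In 5.3.5.4, the restrictive sentence closes a paragraph about isolated abnormalities left to judgment, and the compulsory list stays in force. Repeats are meant to be prompt, so the value may not have been corrected by then.

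There are also safeguards. Suspected infusion-related reactions and Hy's-law cases go to the sponsor within 24 hours even when non-serious (Sections 5.2.3 and 5.4). Duration of hospitalization is a secondary endpoint. The safety-cohort review sees chemistry results directly, and potassium given would appear among concomitant medications.

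Most of this stands, and it rules out a stronger inference that a reader might draw: that the recording rules override the definitions, so that index-stay events go unreported and treated abnormalities are not captured at all. No passage gives the narrower sentences precedence, Section 5.3.1 keeps index-stay events reportable, and Section 6.5 keeps the laboratory data.

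The reply does not remove the conflict. A harmonising reading exists for each sentence, but the protocol does not state it, and the literal wording of each points the other way. Site staff have to choose.

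**Conclusion.** Both conflicts are present in the current text and should be reconciled. The supported conclusion has two parts, with different consequences.

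1. An adverse event that prolongs the index stay may be classified as non-serious, and so miss 24-hour reporting and the SAE summary, when no other seriousness criterion applies.
2. A laboratory abnormality that caused symptoms or was treated, and is normal on repeat, may not be recorded as an adverse event, although its value is captured and analysed.

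Both rest on sites following the literal sentence; the documents do not show how sites read it.

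The size cannot be estimated. Two figures might tempt a reader to try.

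- Section 1.1 gives hospital stays of 5–9 days. That is a background range for hospitalized influenza, measured over the stay and not from dosing. With infusion up to 2 days after admission, it would leave between 5 − 2 = 3 and 9 − 0 = 9 days in hospital after dosing. It describes exposure time, not numbers of affected events.
- In the first-in-human study (Section 1.2.2.1), two laboratory abnormalities were recorded as treatment-emergent events and "Both results returned to normal within 10 days". One was on placebo and neither is said to have been treated. They were recorded, so they are not examples of missed events.

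**What to change.** - **Section 5.3.5.10:** replace the parenthesis with wording that agrees with 5.2.2, so that the status of an adverse event that prolongs the index study hospitalization is unambiguous. Say in the same place that deterioration anticipated from influenza stays under Section 5.3.5.9, so that a long stay from the expected course of the disease does not become an SAE.
- **Section 5.3.5.4:** limit the restrictive repeat-test sentence to isolated abnormalities assessed under the fourth, investigator-judgment criterion. State that the other three criteria apply whatever the repeat result, which agrees with Section 5.2.1.

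The cost is two sentences in an amendment and a memo to sites. The downside is somewhat more SAE and AE forms.

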5.3.5.11 Adverse Events Associated with an Overdose

An overdose is the accidental or intentional use of a drug in an amount higher than the dose being studied. An overdose or incorrect administration of study treatment is not itself an adverse event, but it may result in an adverse event. All adverse events associated with an overdose or incorrect administration of study drug should be recorded on the Adverse Event eCRF. If the associated adverse event fulfills serious criteria, the event should be reported to the Sponsor immediately (i.e., no more than 24 hours after learning of the event; see [Section 5.4.2](#)).

No clinical safety data related to overdosing of MHAA4549A are available, however, overdoses with a monoclonal antibody theoretically could cause volume overload that can result in edema and/or heart failure.

5.4 IMMEDIATE REPORTING REQUIREMENTS FROM INVESTIGATOR TO SPONSOR

Certain events require immediate reporting to allow the Sponsor to take appropriate measures to address potential new risks in a clinical trial. The investigator must report such events to the Sponsor immediately; under no circumstances should reporting take place more than 24 hours after the investigator learns of the event. The following is a list of events that the investigator must report to the Sponsor within 24 hours after learning of the event, regardless of relationship to study drug:

- Serious adverse events (see [Section 5.4.2](#) for further details)
- Non-serious adverse events of special interest (see [Section 5.4.2](#) for further details)
- Pregnancies (see [Section 5.4.3](#) for further details)

The investigator must report new significant follow-up information for these events to the Sponsor immediately (i.e., no more than 24 hours after becoming aware of the information). New significant information includes the following:

- New signs or symptoms or a change in the diagnosis
- Significant new diagnostic test results
- Change in causality based on new information
- Change in the event's outcome, including recovery
- Additional narrative information on the clinical course of the event

Investigators must also comply with local requirements for reporting serious adverse events to the local health authority and IRB/EC.

5.4.2.1 Events That Occur prior to Study Drug Initiation

After informed consent has been obtained but prior to initiation of study drug, only serious adverse events caused by a protocol-mandated intervention should be reported. A paper *Clinical Trial Serious Adverse Event / Adverse Event of Special Interest Reporting Form* should be completed and faxed or scanned and emailed to the Sponsor's Safety Risk Management department or its designee immediately (i.e., no more than 24 hours after learning of the event), using the contact information below per region:

Region	Fax Number	Email Address
Asia Pacific	[REDACTED]	[REDACTED]
Europe	[REDACTED]	[REDACTED]
Latin America	[REDACTED]	[REDACTED]
North America	[REDACTED]	[REDACTED]

5.4.2.2 Events That Occur after Study Drug Initiation

After initiation of study drug, serious adverse events and non-serious adverse events of special interest will be reported until the patient *completes the study* at Day 60 or *discontinues early*. Investigators should record all case details that can be gathered immediately (i.e., within 24 hours after learning of the event) on the Adverse Event eCRF and submit the report via the electronic data capture (EDC) system. A report will be generated and sent to Safety Risk Management by the EDC system.

In the event that the EDC system is unavailable, a paper *Clinical Trial Serious Adverse Event/Adverse Event of Special Interest Reporting Form* should be completed and faxed or scanned and emailed to *the Sponsor* or its designee immediately (i.e., no more than 24 hours after learning of the event), using the contact information provided to investigators (see [Section 5.4.2.1](#)). Once the EDC system is available, all information will need to be entered and submitted via the EDC system.

Instructions for reporting post-study adverse events are provided in [Section 5.6](#).

